**HANDOUT 5: Environmental Sound Devices**

A wide variety of environmental sound devices exist that help mask tinnitus. These can be used in your normal work, living, and sleep environments. Devices that emit a white noise signal are available as are those that produce simulated sounds such as rain, a stream, and other nature sounds. Recorded nature sounds are also available from many sources on CD or for MP3 or iPOD downloads. Another popular device is the tabletop water fountain that provides an ongoing background sound appropriate for an office or living room setting. You can easily access information about such devices on the internet and search for white noise, nature sounds, or sleep devices. Below are just a few examples of available devices that you can find on the websites listed in the resource handout.

[Sound Oasis Sound Therapy System](#)[Marpac Sleep-Mate/Sound Screen](#)[Sound Oasis Sound Therapy Pillow](#)[Marsona Travel Sound Conditioner](#)[Alpine Eternity Tabletop Fountain](#)[Homedics Portable Sound Spa](#)

---

## HANDOUT 6: Website Resources

### Sleep

<http://www.mayoclinic.com/health/sleep/HQ01387>  
[http://www.helpguide.org/life/sleep\\_tips.htm](http://www.helpguide.org/life/sleep_tips.htm)  
<http://www.sleepfoundation.org/article/sleep-topics/healthy-sleep-tips>  
<http://www.selfhelpmagazine.com/article/insomnia>

### Relaxation

[http://helpguide.org/mental/stress\\_relief\\_meditation\\_yoga\\_relaxation.htm](http://helpguide.org/mental/stress_relief_meditation_yoga_relaxation.htm)  
<http://www.mayoclinic.com/health/relaxation-technique/SR00007>  
<http://www.squidoo.com/7relaxationtips>  
<http://www.webmd.com/balance/stress-management/features/blissing-out-10-relaxation-techniques-reduce-stress-spot>

### Concentration

<http://www.counselling.cam.ac.uk/concen.html>  
<http://zenhabits.net/5-tips-to-maximize-your-ability-to-concentrate/>  
<http://www.lumosity.com/>  
<http://www.getselfhelp.co.uk/docs/ATT.pdf> (attention training techniques)

### Environmental Sound Devices

<http://www.sleepwellbaby.com/Natural-Sound-Machines-s/462.htm>  
<http://www.serenitysupply.com/>  
<http://www.target.com/> (Search on “white noise” for many of these devices)  
<http://www.soundmachinesdirect.com/>  
<http://www.white-noise.us/>  
<http://www.sound-oasis.com/>  
<http://www.marpac.com/>

### Nature Sound Downloads

<http://www.calmsound.com/>  
<http://www.naturesounds.ca/>  
<http://www.soundsleeping.com/>  
<http://itunes.apple.com/us/artist/nature-sounds/id188943426>

---

## **14.1 Introduction**

Data collection forms comprise the main source of data flowing from the Clinical Centers to the Data Coordinating Center (DCC). The uniform collection of data from Clinical Centers is crucial to the overall quality of the trial. The data collection forms have been developed to obtain information in an unambiguous, straightforward manner. In the following pages, information about the general format of the Tinnitus Retraining Therapy Trial (TRTT) data collection forms is provided, along with instructions for how forms will be filled out for each patient during the eligibility visit, treatment, and during treatment follow-up.

## **14.2 General Information**

### **14.2.1 Obtaining Forms**

Forms are developed by the DCC in conjunction with the TRTT database that will be used for analyses. The forms are reviewed by both the Steering Committee (STC) and the Data and Safety Monitoring Board (DSMB), and then tested at selected Clinical Centers prior to general use.

Printable copies of each data collection form will be available on the TRTT website. Data collection forms will be organized by type of visit on the TRTT website. In preparation for a study visit, Clinical Center Coordinators should print out the required forms. As revised forms are generated, these will be posted on the TRTT website to replace the original version of the form. The revision number and date of revision for every form is found both in Section A and at the bottom of each page of the form. The DCC will notify each Clinical Center by email memorandum whenever a more recent revision is to be used. The Clinical Coordinator is responsible for seeing that all forms used are the most current version.

### **14.2.2 General Guidelines for Filling Out Forms**

Only fully certified TRTT Clinical Center staff may fill out TRTT data collection forms. Non-certified personnel and personnel certified for only certain procedures may not complete TRTT forms. Restricting completion of forms to TRTT certified personnel will maintain the same level of quality in data collection throughout all Clinical Centers and the integrity of the data. Since Clinical Center staff will be entering the data online at the TRTT website, it is important that all entries are legible. For questions in which there is a series of yes/no answers, and all responses are yes or no, vertical lines may be drawn through the appropriate answers as a quicker alternative to checking each line individually. A blue or black pen should be used to fill out forms (never a pencil). If an error is made in filling out a form, then corrections may be made using a different colored (e.g., red) pen. Do not use white-out or try to erase or obliterate the original answer. Cross out the incorrect answer with a single line, write the correct answer in a space near the incorrect answer, and initial and date the new entry. Both the correct and the incorrect answer should be legible.

While entering dates, Clinical Center staff must make every attempt to obtain an accurate date. Sometimes, however, the Study Participant may not remember an exact date (e.g., when a medication was last used). For example, the Study Participant may be able to remember the year of an event, but not recall the month or day. If this is the case, first probe for the month by asking the Study Participant to try and remember the season, then the month, and finally the day.

If the Study Participant is unable to remember the year, probe by asking the Study Participant to try and remember some other event that took place about the same time or ask the Study Participant to recall about how many years ago the event took place. Enter only the date components that the Study Participant is able to recall.

All forms should be checked for accuracy and completeness before being entered on the TRTT website. A thorough review of the form before it is entered on the TRTT website will increase efficiency at the Clinical Center. Because correcting omissions or errors found at the time of data entry uses tremendous resources, the Clinical Coordinator should attempt to make sure forms are complete and correct before beginning the data entry process.

All forms except the first page will have a space on the top right-hand corner in which to enter the Patient ID. This information must be entered on every page of all forms, so that if the pages of a form become separated, it is clear to whom the data refer. The reference number on the first page is used to record the data entry confirmation number when the form is data entered in the TRTT database.

The person responsible for obtaining the information on the form is the one whose name should be provided as the person completing the form. That person's certification number must also be on the form. The certification number comprises a series of three digits and is assigned at the time of certification.

Some data collection forms are completed by the Study Participant. The Clinical Coordinator or Study Audiologist should complete the administrative Section A before providing the self-report form to the Study Participant with appropriate instructions. After completion of a self-report form, the Clinical Coordinator should review the form for completeness and attempt to obtain responses for any missing values. The Clinical Coordinator should then complete the final administrative section on the self-report form. In cases where a Study Participant is not available for completion of a study visit, then copies of all self-report forms should be sent to the Study Participant by U.S. Postal Service for completion along with a stamped self-addressed envelope to return completed forms.

#### **14.2.3 Transmitting Data to the Coordinating Center**

Once a form is completed, signed, and checked for accuracy and completeness, it is ready for data entry using the TRTT website. The Clinical Coordinator will enter all forms into the website following the procedures outlined in the TRTT Website Use Handbook and described during training. In general, data entry is restricted to individuals who have completed training in using the website and been assigned usernames and passwords to access the data entry portion of

the TRTT website. The Eligibility Checklist is used to “register” a Study Participant in the data system. It must be completed and entered in the data system before any other data collection forms can be entered, including those used to request a randomized treatment assignment. All other Study Forms must be entered within a week following completion of the Study visit.

There will be occasions when TRTT staff at the Clinical Center need to change or update a data item. These types of changes are implemented by accessing the data system, calling up the original data entry screen by use of the reference number assigned to that form, and changing or entering the correct variable.

#### **14.2.4 Filing Forms**

Each Clinical Center must maintain a file for TRTT materials. Included in the file is correspondence from and to the Coordinating Center, General Hearing Instruments, Inc., and the Study Chair’s Office. Materials related to the Cooperative Research and Development Agreement (CRADA) and the Institutional Review Board (IRB) correspondence should also be included. There should be locked files for Study Participant files. It is important that participant confidentiality be preserved and access to the locked participant files be restricted to study personnel. The Clinical Coordinator should maintain the files.

### **14.3 Instructions for Eligibility Forms**

The following will provide detailed instructions for completion of data collection forms related to screening and determining eligibility of potential study participants. The forms are in approximate sequential order relative to enrollment and follow-up. The Eligibility Screening Form serves to “register” a potential study participant in the TRTT and must be entered before any other data collection form can be entered online.

If it is determined that a potential participant is ineligible at any point in the process of completing the baseline eligibility forms, no further forms need be completed. Rather, the Eligibility Checklist is completed, indicating the reason(s) for ineligibility. Partially or fully completed forms on ineligible individuals, except for the Eligibility Screening Form, should not be entered in the TRTT online database nor kept in the TRTT Clinical Center participant files.

Descriptions of some of these forms and instructions for completion are also included in Chapters 5, 6 and 9.

### **14.3.1 Eligibility Screening Form**

The Eligibility Screening Form (ES) is used to screen potential study participants with tinnitus on a few easily determined eligibility criteria and determine potential eligibility for the TRTT. The Eligibility Screening Form is completed by the Clinical Coordinator over the telephone or in-person for persons who have been referred to the TRTT. The namecode and study ID that is used throughout the study is assigned at screening by obtaining a pre-printed label from the sheet of study IDs provided by the DCC and affixing the label to the ES form. If the individual fails any of the eligibility criteria in Section B, then he or she is not eligible for the TRTT. If the individual fulfills all the eligibility criteria, a Baseline Eligibility Visit is scheduled. The Eligibility Screening Form must be entered on the online database regardless of eligibility because it “registers” the individual and also provides demographic information of all persons considered for the study.

### **14.3.2 Patient Locator Form**

The Patient Locator Form is used to record the Study Participant’s contact information for clinic records. It is completed for all eligible Study Participants at the Baseline Eligibility Visit and at any subsequent visit as needed to update information. The Clinical Coordinator completes the form, recording various information such as the Study Participant’s contact information, primary physician contact information, and emergency contact(s). The form is not entered online or ever sent to the DCC, but is filed in the Study Participant’s TRTT file at the Clinical Center.

### **14.3.3 Tinnitus Questionnaire**

The Tinnitus Questionnaire (TQ) is completed by the Study Participant at the Baseline Eligibility Visit to evaluate eligibility and provide the baseline value for comparison at follow-up. It is also completed at all subsequent follow-up visits. The TQ evaluates five domains of health related quality of life affected by the presence of tinnitus. The TQ is scored using a separate scoring sheet provided to Clinical Centers because not all items are scored in the same direction. A score of less than 40 on the TQ at the initial screen will exclude the potential participant from the TRTT. The Clinical Coordinator or Study Audiologist should enter the ID codes for the Study Participant, study visit dates, and review the completed form to make sure all items have been completed. The TQ is described in detail in Chapter 9.

#### **14.3.4 Beck Depression Inventory Fast Screen**

The Beck Depression Inventory Fast Screen (BD) is completed by the Study Participant during the Baseline Eligibility Visit as a screen for clinical depression. A total score of 4 or greater or a score of either 2 or 3 on item 7 will signal the need for further evaluation of the potential Study Participant for the presence of clinical depression. This form is also completed at each Follow-up Visit as a means to monitor depression as an Adverse Event. The Clinical Coordinator or Study Audiologist should enter the ID codes for the Study Participant, enter the study visit dates, and review the completed form to make sure all items have been completed.

#### **14.3.5 Tinnitus History Form**

The Tinnitus History Form (TH) is completed by the Study Audiologist or the Clinical Coordinator at the time of the Baseline Eligibility Visit for each individual who is being considered for entry into the TRTT. Information collected on this form includes data on inclusion and exclusion criteria and also baseline tinnitus variables.

#### **14.3.6 Medical History Form**

The Medical History Form (MH) is completed by the Study Otolaryngologist, Study Audiologist, or the Clinical Coordinator at the time of the Baseline Eligibility Visit for each individual who is being considered for entry into the TRTT. If the form is not completed by the Study Otolaryngologist, it must be provided to him/her for review. Information collected on this form includes data on inclusion and exclusion criteria and also baseline health and medical variables.

#### **14.3.7 Baseline Tinnitus Retraining Therapy Interview Form**

The Baseline Tinnitus Retraining Therapy Interview Form (BT) is completed by the Study Audiologist at the time of the Baseline Eligibility Visit for each individual who is being considered for entry into the TRTT. Text in *italics* is read by the interviewer to the individual to guide him or her through the interview. This form is used to obtain a description of the individual's tinnitus, sound tolerance, and hearing status and the impact of each of these components on the Study Participant's health-related quality of life. Results from the interview serve as the basis to categorize each Study Participant into one of Jastreboff's TRT patient categories. Details for completing this form are included in Chapter 6.

### **14.3.8 Audiological/Tinnitus/Hyperacusis Form**

The Audiological/Tinnitus/Hyperacusis Form (BA) is completed by the Study Audiologist at the time of the Baseline Eligibility Visit for each individual who is being considered for entry into the TRTT. Data on the Study Participant's audiological testing, tinnitus characteristics, and sound tolerance are recorded on this form as well as results of tests related to exclusion criteria based on objective tinnitus.

### **14.3.9 Physical Examination Form**

The Physical Examination Form (PH) is completed by the Study Otolaryngologist at the time of the Baseline Eligibility Visit for each individual who has completed the Medical History and is being considered for entry into the TRTT. Results of measures related to inclusion and exclusion criteria obtained on the physical examination are recorded on this form.

### **14.3.10 Laboratory and Other Tests Form**

The Laboratory and Other Tests Form (LO) is completed by the Study Otolaryngologist at the time of the Baseline Eligibility Visit for each individual who has completed the Physical Examination, to record whether additional tests were required, including blood tests, imaging tests, or tests to assess emotional, psychological, or psychiatric health. Results of measures related to inclusion and exclusion criteria obtained on these tests are recorded on this form.

## **14.4 Instructions for Forms used to Summarize Eligibility Status**

### **14.4.1 Eligibility Checklist Form**

The Eligibility Checklist Form (EC) is completed by the Clinical Coordinator to assess the eligibility of every potential Study Participant for randomization to the TRTT. The numbers in parentheses at the end of each question refer to the number of the corresponding question of the data collection form that is recorded as the section heading. A "Yes" or "No" response is checked for each eligibility criterion. If no shaded boxes are checked, then the patient is eligible for randomization and a randomized treatment assignment may be requested using the online randomization process provided by the DCC.

Any response in a shaded box indicates that the patient is not eligible for randomization or not eligible at this time, i.e., pending eligibility. The Clinical Coordinator should complete those sections of the Eligibility Checklist corresponding to those parts of the Baseline Eligibility Visit

that had been attempted or completed. At least one reason for ineligibility must be checked, but all known reasons should be entered.

#### **14.4.2 Pending Study Participant Status Form**

A Pending Study Participant Status Form (PE) is used to notify the DCC that a potential Study Participant is not eligible at this time due to the presence of one or more pending eligibility criteria. This form records the date when the potential Study Participant will have fulfilled that criterion and may be re-evaluated for participation in the TRTT, and is used by the DCC to send reminders to the Clinical Center when the pending criterion may no longer apply.

### **14.5 Instructions for Self-Report and Cognitive Forms Completed at Randomization**

#### **14.5.1 Tinnitus Handicap Inventory**

The Tinnitus Handicap Inventory (TI) is completed by the Study Participant after indicating his/her agreement to allow randomization in the TRTT, but before the randomized treatment assignment is requested. This form evaluates health-related quality of life domains affected by tinnitus in addition to those assessed by the TQ, and is also completed at all subsequent follow-up visits. The Clinical Coordinator or Study Audiologist should enter the ID codes for the Study Participant, enter the study visit dates, and review the completed form to make sure all items have been completed. A full description of this form is included in Chapter 9.

#### **14.5.2 Tinnitus Functional Index**

The Tinnitus Functional Index (TF) is completed by the Study Participant after indicating his/her agreement to allow randomization in the TRTT, but before the randomized treatment assignment is requested. This form evaluates health-related quality of life domains affected by tinnitus in addition to those assessed by the TQ, and is also completed at all subsequent follow-up visits. The Clinical Coordinator or Study Audiologist should enter the ID codes for the Study Participant, enter the study visit dates, and review the completed form to make sure all items have been completed. A full description of this form is included in Chapter 9.

#### **14.5.3 Digit Symbol Substitution Task**

The Digit Symbol Substitution Task (DS) is completed by the Study Participant after indicating his/her agreement to allow randomization in the TRTT, but before the randomized treatment assignment is requested. This form is also completed at the 6-month and 18-month follow-up visits in the TRTT. The DS is a neuropsychological test that assesses the ability of the

Study Participant to concentrate on a psychomotor task. The Clinical Coordinator or Study Audiologist must administer this test to the Study Participant. The DS is described further in Chapter 9.

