#### **14.6.5 Loudness Discomfort Level Assessment for Treatment Form**

The Loudness Discomfort Level (LDL) Assessment for Treatment Form (LD) is completed by the Study Audiologist who is not involved in the treatment of the Study Participant (i.e., who is blinded to the TRTT assignment). It is used to measure the LDL in order to provide information for treatment. It is completed at the second treatment visit (T2) and at the 3-month Follow-up Visits (F1). The Follow-up ATH form includes LDL measurements and is completed during subsequent Follow-up Visits.

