### **14.7.3 Follow-up Audiological/Tinnitus/Hyperacusis Form**

The Follow-up Audiological/Tinnitus/Hyperacusis Form is completed by the Study Audiologist at the 6, 12, and 18 months Follow-up Visits. Data on the Study Participant's audiological testing, tinnitus characteristics, and sound tolerance are recorded on this form.

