#### **17.2 Personnel Certification**

##### **17.2.1 Positions Requiring Certification**

TRTT certification is required for each of the following study roles:

- Clinical Coordinator;
- Data System Operator;

- Study Otolaryngologist; and
- Study Audiologist.

Two Study Audiologists at each Clinical Center will be required to allow one to conduct the counseling session (directive counseling (DC) or standard of care clinical consultation (SC)) for a particular Study Participant while the other will remain blinded to that participant's treatment assignment.

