#### **18.4.2.2 Responsibilities**

The Clinical Coordinator, together with the Clinical Center Director, is responsible for ensuring that the Clinical Center is ready for participation in the TRTT. Specific duties of the Clinical Coordinator related to preparation and ongoing maintenance of Clinical Center activities include:

- Attending scheduled TRTT training sessions;
- Ensuring all Study Audiologists have the requisite training and competence necessary for the provision of DC and sound therapy in accordance with the trial protocol;
- Ensuring all Study Audiologists have the requisite training in SC treatment to ensure uniform administration across all Clinical Centers;
- Serving as a resource for other study personnel regarding the details of the TRTT protocol;
- Initiating and maintaining all required communications with the relevant institutional review board concerning the TRTT protocol implementation at the Clinical Center and documentation for informed consent and HIPAA;
- Monitoring levels of supplies to guard against shortages during the data collection process; and
- Maintaining all Clinical Center communication including correspondence, e-mail, and telephone inquiries regarding the TRTT.

Responsibilities of the Clinical Coordinator include tasks related to participant interactions, include:

- Implementing methods for recruitment of appropriate Study Participants;
- Verifying each participant's eligibility for participation in the trial;
- Ensuring that sufficient numbers of Study Participants are being recruited;
- Maintaining documentation related to Study Participants, including:
  - appointment notebooks with each participant's follow-up schedule; and
  - log book with Study Participant ID numbers, and namecode;
- Conducting the necessary Study Participant education and obtaining informed consent from Study Participants;
- Coordinating the treatment modules for Study Participants following their randomized assignments;
- Overseeing administration of self-report measures upon enrollment in the trial;
- Sending Study Participants appointment reminders with date and time noted;
- Updating each participant's records with change of address, employment site and other relevant contact information;
- Contacting Study Participants to maintain their interest in the trial between scheduled visits, thereby demonstrating the investigator's ongoing concern for the Study Participant;

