### **23.1.2 Primary Objective**

The primary objective of the TRTT is to assess the efficacy of TRT, defined as DC and ST achieved through conventional SGs (Group 1) as a treatment for severe debilitating tinnitus. The primary outcome to be measured in the TRTT is the difference in scores on the Tinnitus Questionnaire (TQ) between baseline and follow-up assessed longitudinally, at 3, 6, 12, and 18 months of treatment. The corresponding hypothesis is that TRT (Group 1 in Table 22.1) compared with the standard of care (SC; Group 3) will reduce the severity of debilitating tinnitus significantly as assessed by longitudinal changes in the TQ score and at the end of treatment..

The secondary efficacy outcomes will test the following hypotheses. TRT (Group 1) compared with SC (Group 3) will reduce severity of debilitating tinnitus significantly as assessed by longitudinal changes in:

Score on the following tinnitus and functional measures:

- Sub-scales of the TQ;
- Tinnitus Handicap Inventory;
- Tinnitus Functional Index;
- TRT Visual Analogue Scale; and
- Digit Symbol Substitution Task.

and psychoacoustic measures:

- Tinnitus Pitch and Loudness Match; and
- Loudness Discomfort Level (LDL)

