### **23.3.2.2 Secondary Efficacy Analyses**

For the analyses looking at the difference between TQ score at baseline and 18 months, we will compare TQ mean scores at 18-month in the treatment phase among treatment groups using Analysis of Covariance (ANCOVA). We will adjust for Baseline TQ scores and heterogeneity of

tinnitus status in the patient population. We will also adjust for important baseline covariates and variables that may be unbalanced at baseline (even with randomization) and are potentially related to TQ score. We will also use GEE for this analysis.

The data resulting from this project will enable us to address a number of additional research questions. First, to assess the effect of the interventions on different aspects of tinnitus morbidity, we will use the approach described above with other outcome variables, including the TQ subscales, global and subscale scores of the Tinnitus Functional Index, the Tinnitus Handicap Inventory, and the visual analog scale of the TRT Interview instrument. We will also compare baseline audiometric measures, and psychoacoustic variables of Tinnitus Loudness Match and Loudness Discomfort Level to evaluate whether there is any change across time in these measures.

The secondary outcome variables are the same for both the primary objective and the secondary objectives. For both the objectives, all of the longitudinally assessed variables (for example, subscales of TQ, Tinnitus Handicap Inventory, Tinnitus Functional Index, TRT-Visual Analog Scale, Digit Symbol Substitution Task, tinnitus pitch and loudness match, and LDL) will be treated as the TQ score (primary efficacy outcome analysis) using GEE. The respective mean scores will be compared between corresponding treatment groups (as described in the previous section) over the entire treatment phase. Both the differences in mean responses between treatment groups and the rate of change over time will be of interest in these analyses.

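### Section 14.5.3 does not require whoever gives the 6- and 18-month Digit Symbol Substitution Task to be blinded to TRT versus standard of care, although a blinded audiologist is already required for each participant

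*Combined protocol and SAP*

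**What the plan says.** Section 14.5.3 describes the DSST as a neuropsychological test of concentration on a psychomotor task. It is done once before the treatment assignment is requested. After that, "This form is also completed at the 6-month and 18-month follow-up visits in the TRTT". On who gives it, the section says: "The Clinical Coordinator or Study Audiologist must administer this test to the Study Participant". It states no blinding condition and refers to Chapter 9 for further description.

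Sections 23.1.2 and 23.1.3 list the "Digit Symbol Substitution Task" among the secondary efficacy outcomes for all three group comparisons. Section 23.3.2.2 gives the analysis: the longitudinal secondary variables, including "Digit Symbol Substitution Task, tinnitus pitch and loudness match, and LDL) will be treated as the TQ score", are modelled by GEE.

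On staffing, section 17.2.1 requires two Study Audiologists per center, so that one counsels the participant "while the other will remain blinded to that participant's treatment assignment". Section 18.4.2.2 lists among the Clinical Coordinator's duties: "Coordinating the treatment modules for Study Participants following their randomized assignments". Sections 12.2 and 23.1.1 keep the type of sound generator, conventional or placebo, hidden from audiologists and participants.

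**The concern.** For the neighbouring instruments (14.5.1, 14.5.2 and 14.5.4, for example), staff fill in identifiers and dates and check for blanks, and the participant does the rest. The DSST is different because a member of staff has to run it. How the task is introduced and how much encouragement is given could depend on what that person believes about the treatment. If the administrator knows TRT from SC, such differences line up with the randomized groups and enter the estimated effect.

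Most efficacy outcomes here are self-reported by participants who know which kind of counseling they had, and blinding staff cannot change that. The DSST is one of the few outcomes where a blinded administrator can remove a source of bias. Unblinded administration is hard to repair afterwards. The audiologist terms in the model of section 23.3.2.1 are main effects. They absorb differences between audiologists, but not one audiologist treating TRT and SC participants differently.

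**Working it through.** The plan states no figure on this point, so the check is mainly a comparison of sections.

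**Who may give the test, and what they know**

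| Permitted person | Knowledge of TRT versus SC | Knowledge of conventional versus placebo device |
|---|---|---|
| Treating audiologist | Yes: delivers the assigned counseling (14.6.2, 14.6.3, 16.5.2) | No, by design (12.2, 23.1.1) |
| Clinical Coordinator | Inferred: coordinates treatment by assignment (18.4.2.2), may order the devices (12.2.1), may complete the Treatment Start-up Form (14.6.1), enters all forms (14.2.3) | No source found; logged device output is encrypted at the center (21.3.5) |
| Second audiologist | No, by requirement (17.2.1) | No |

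Section 14.5.3 permits all three and states no preference.

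**Which comparisons are exposed**

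- Group 1 versus Group 3 (TRT versus SC): exposed.
- Group 2 versus Group 3 (counseling with placebo device versus SC): exposed.
- Group 1 versus Group 2: not exposed, because both groups get the same counseling and device type is masked.

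**Which visits are exposed**

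Only 6 and 18 months. The baseline test precedes the assignment, so knowledge of it cannot play a part.

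**The plan's own practice elsewhere**

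Section 14.6.5 gives the loudness discomfort form at the one-month treatment visit and at 3 months, which serves treatment, to an audiologist "who is not involved in the treatment of the Study Participant (i.e., who is blinded to the TRTT assignment"). Appendix D (Script for Follow-up Counseling, Part 2) says a blinded audiologist completes the Follow-up TRT Interview. So the plan uses blinded assessment where it names it. For the DSST it names a wider set of people.

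**Illustration of sensitivity**

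The shift is assumed, since the documents give none.

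- Number per arm: 76 less 10% attrition (23.2.3) = 76 × 0.90 = 68.4, taken as 68.
- Standard error of a two-group difference at one visit, in SD units: √(2/68) = 0.171.
- Assumed shift 0.1 SD: 0.1/0.1715 = 0.583 standard errors. A two-sided t-test at 5% with 134 degrees of freedom then rejects in 8.9% of trials with no true effect.
- Assumed shift 0.2 SD: 0.2/0.1715 = 1.166 standard errors, and the rejection rate is 21.2%.

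The shift means the average difference between arms. If only half the sessions were given by someone who knew the assignment, a 0.2 SD effect in those sessions would average 0.2 × 0.5 = 0.1 SD. The calculation covers one visit, whereas the plan analyses the DSST longitudinally.

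**The case against.** The strongest reply is that silence in Chapter 14 does not prove there is no rule. Only the second part of the manual was available. Section 14.5.3 points to Chapter 9, and follow-up procedures are in Chapter 10; neither was seen. Chapter 14 also demonstrably leaves out blinding rules stated elsewhere: section 14.7.2 assigns the Follow-up TRT Interview simply to the Study Audiologist, while Appendix D assigns it to the blinded one. This stands as a limit on the point but does not remove it. Section 14.5.3 goes beyond shorthand because it expressly admits the Coordinator. If Chapter 9 does require blinding, the two texts conflict and 14.5.3 still needs editing.

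The same argument defeats an extension that a reader might make to section 14.7.3. The follow-up audiological form, which includes the loudness discomfort levels, "is completed by the Study Audiologist at the 6, 12, and 18 months Follow-up Visits". That is the wording used for the interview, where it can mean the blinded audiologist, and 14.6.5 presents the later discomfort-level testing as continuing on that form. The documents do not support a claim that those outcomes lack blinded assessment.

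The Coordinator's knowledge is an inference. Section 22.2.4 says the randomization report shows only a kit ID, with the assignment inside the kit. Against that, the duties listed above make ignorance of TRT versus SC unlikely, and no available section requires the Coordinator to be blinded. The treating audiologist's knowledge needs no inference.

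Finally, the available text gives no instructions, timing or scoring for the task, so how much room an administrator has to influence the score is not documented. This stands.

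**Conclusion.** The point holds in a limited form. As written, section 14.5.3 allows the 6- and 18-month DSST to be given by someone who knows TRT from SC, when a blinded audiologist must already exist for that participant. The direction and size of any resulting bias are unknown. The rates of 8.9% and 21.2% show only what an assumed shift would do and are not estimates for this trial.

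A reader might infer that these staff know the full three-way allocation and that every DSST comparison is compromised. The documents do not support that: device type is masked, so Group 1 versus Group 2 is protected. A reader might also infer a threat to the trial's main result. That does not follow either: the TQ is completed by the participant (14.3.3), and the sample size is set on it (23.2). The point concerns one secondary outcome in two of three comparisons. It is worth acting on because the correction is cheap.

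It assumes that Chapters 9 and 10 contain no overriding rule, and that the Coordinator's listed duties reveal the assignment.

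**What to change.** In section 14.5.3, add that at 6 and 18 months the DSST is administered by the Study Audiologist who is blinded to that participant's assignment, and that any other administrator is logged on the Protocol Deviation Form (14.8.7). Leave the baseline rule as it is. Check the new sentence against the DSST description in Chapter 9 and the follow-up procedures in Chapter 10, and make them agree.

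No new recording is needed. Section 14.2.2 already requires the certification number of the person obtaining the data, and section 16.6 already treats departures from protocol as violations to be documented. No extra staff are needed, because section 17.2.1 already requires the second audiologist. The cost is slightly less freedom in scheduling the two visits, since the Coordinator or treating audiologist could no longer step in without a deviation being recorded.
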